8.4.3 Electrocardiogram

For the following ECG measurements during the TE Period of OL-SS, a summary of observed values and change from baseline values will be provided at each visit (in msec): RR interval, PR interval, QT interval, and QTcF interval, QRS duration, and Heart Rate (beats per minute).

The number and percentage of subjects meeting at least 1 threshold analysis criterion during the TE Period of OL-SS will be summarized overall. The threshold analysis criteria are provided in [Appendix E](#).

8.4.4 Vital Signs

For the vital sign measurements during the TE Period of OL-SS, the observed values and change from baseline values will be summarized at each visit. The following vital signs parameters will be summarized: systolic and diastolic blood pressure (mm Hg), body temperature ($^{\circ}$ C), pulse rate (beats per minute), and respiratory rate (breaths per minute).

The number and percentage of subjects meeting at least 1 threshold analysis criterion during the TE Period will be summarized. The threshold analysis criteria are provided in [Appendix E](#).

In addition, a listing containing individual subject vital signs values will be provided. This listing will include data from both scheduled and unscheduled visits.

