8 STATISTICAL ANALYSIS

8.1 General Considerations

The precision standards for reporting safety variables are provided in an internal Biometrics document that specifies the programming rules including the precision for derived variables.

The Schedule of Assessments is provided in Section 3 of CSP.

Continuous variables will be summarized using the following descriptive summary statistics: the number of subjects (n), mean, standard deviation (SD), median, minimum value (min), and maximum value (max).

Categorical variables will be summarized using counts and percentages. Percentages will be presented to 1 decimal place.

The **baseline value**, unless otherwise specified, for the long-term safety analysis will be the **TC safety baseline**, defined as the most recent non-missing measurement (scheduled or unscheduled) collected before the first dose of ELX/TEZ/IVA either in the parent study or the open label study, as applicable. The baseline value for the long-term efficacy analysis, unless otherwise specified, will be the **parent study baseline**, defined as the most recent non-missing measurement (scheduled or unscheduled) collected before the first dose of study drug in the parent study. For assessments collected in duplicate or triplicate, the baseline will be defined as the average of non-missing values.

Absolute change from baseline will be calculated as post-baseline value - baseline value.

Relative change from baseline will be calculated and expressed in percentage as $100\% \times (\text{Post-baseline value} - \text{Baseline value}) / \text{Baseline value}$.

Treatment-emergent (TE) Period will include the time from the first dose date of study drug in the OLE to 28 days after the last dose of the study drug in the OLE or to the date of completion of study participation (as defined in CSP Section 9.1.5), whichever occurs first.

Unscheduled visits: Unscheduled visit measurements will be included in analysis as follows:

- 1) In scheduled visit windows per specified visit windowing rules
- 2) In the derivation of baseline and last on-treatment measurements
- 3) In the derivation of maximum and minimum values during TE period, and maximum and minimum change from baseline values during TE period for safety analyses
- 4) In individual subject data listings as appropriate

Visit windowing rules: The analysis visit windows for protocol-defined visits are provided in [Appendix A](#).

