8.2.2 Demographics and Baseline Characteristics

Demographics and baseline characteristics will be summarized based on the OL-FAS and presented by treatment group in the parent study and overall.

Demographic data from the parent study (445-116) will include the following:

- Age at parent study baseline (in years)
- Sex (female and male)
- Ethnicity (Hispanic or Latino, not Hispanic or Latino, and not collected per local regulations)
- Race (White, Black or African American, Asian, American Indian or Alaska Native, Native Hawaiian or Other Pacific Islander, multiracial, and not collected per local regulations)
- Country

Baseline characteristics from the parent study (445-116) will include the following:

- Weight (kg)
- Weight-for-age z-score
- Height (cm)
- Height-for-age z-score
- BMI (kg/m²)
- BMI-for-age z-score

Stratification categories used in the parent study will include the following:

- LCI_{2.5} at Screening Visit (<10, ≥10)
- Weight at Screening Visit (<30, ≥30 kg)

Disease characteristics from the parent study (445-116) baseline will include the following:

- Sweat chloride at parent study baseline (continuous)
- LCI_{2.5} at parent study baseline (continuous)
- ppFEV₁ category at parent study baseline (<70, ≥70 to ≤90, and >90)
- ppFEV₁ at parent study baseline (continuous)

- CFQ-R respiratory domain score at parent study baseline (child 6-11's version, continuous)
- Prior use of dornase alfa (Yes, No)
- Prior use of azithromycin (Yes, No)
- Prior use of inhaled antibiotic (Yes, No)
- Prior use of any bronchodilator (Yes, No)
- Prior use of any inhaled bronchodilator (Yes, No)
- Prior use of any inhaled hypertonic saline (Yes, No)
- Prior use of any inhaled corticosteroids (Yes, No)

Prior medication use definition is same as that for the baseline characteristics summary presented in the parent studies. In addition, data listings will also be provided for:

- Informed consent
- Inclusion/Exclusion criteria violation for subjects with any such violations

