11 LIST OF APPENDICES

Appendix A: Analysis Visit Windows for Safety and Efficacy Assessment

Table 11-1 Analysis Visit Windows for Safety and Efficacy Assessments

Assessment	Visit ¹	Target Study Day	Analysis Visit Window ^{2,3,4} (in study days)
Spirometry Weight, Height and BMI as well as the corresponding z-score	Parent Study Baseline	--	≤1 corresponding to the first dose date of parent study
	OL Week 4	29	(1, 43]
	OL Week 8	57	(43, 85]
	OL Week 16	113	(85, 141]
	OL Week 24	169	(141, 211]
	OL Week 36	253	(211, 295]
	OL Week 48	337	(295, 379]
	OL Week 60	421	(379, 463]
	OL Week 72	505	(463, 547]
	OL Week 84	589	(547, 631]
	OL Week 96	673	(631, 729]
	OL Safety Follow-up	Not applicable	Use nominal visit
Sweat Chloride, LCI _{2.5} , CFQ-R	Parent Study Baseline	--	≤1 corresponding to the first dose date of parent study
	OL Week 4	29	(1, 43]
	OL Week 8	57	(43, 85]
	OL Week 16	113	(85, 141]
	OL Week 24	169	(141, 253]
	OL Week 48	337	(253, 421]
	OL Week 72	505	(421, 589]
	OL Week 96	673	(589, 729]
Hematology Serum Chemistry Pulse Oximetry Vital Signs (excluding Weight, Height and BMI as well as the corresponding z-score)	TC Safety Baseline	1	Defined in Section 8.1
	OL Week 4	29	[1, 43] where day 1 is post-dose measurement
	OL Week 8	57	(43, 85]
	OL Week 16	113	(85, 141]
	OL Week 24	169	(141, 211]
	OL Week 36	253	(211, 295]
	OL Week 48	337	(295, 379]
	OL Week 60	421	(379, 463]
	OL Week 72	505	(463, 547]
	OL Week 84	589	(547, 631]
	OL Week 96	673	(631, 687]
	OL Safety Follow-up ⁴	Not applicable	Use nominal visit
Standard 12-lead ECG	TC Safety Baseline	1	Defined in Section 8.1
	OL Week 8	57	[1, 85] where day 1 is post-dose measurement
	OL Week 16	113	(85, 141]
	OL Week 24	169	(141, 253]
	OL Week 48	337	(253, 421]
	OL Week 72	505	(421, 589]
	OL Week 96	673	(589, 687]
		OL Safety Follow-up ⁴	Not applicable

Table 11-1 Analysis Visit Windows for Safety and Efficacy Assessments

Assessment	Visit ¹	Target Study Day	Analysis Visit Window ^{2,3,4} (in study days)
Coagulation	TC Safety Baseline	1	Defined in Section 8.1
	OL Week 24	169	[1, 253] where day 1 is post-dose measurement
	OL Week 48	337	(253, 421]
	OL Week 72	505	(421, 589]
	OL Week 96	673	(589, 687]

Notes:

¹Visit name for analysis purpose is used to report data in tables and figures.

²The analysis visit windows will be applied using the following rules for both scheduled and unscheduled visits:

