- a. If no numerical measurement is available within a visit window, the measurement will be considered missing for the visit.
- b. If there is more than 1 numerical measurement available within a visit window, use the following rules:
 - i. The measurement closest to the target day will be used; or
 - ii. If there are multiple measurements with the same distance from the target day, the latest measurement will be used. If the latest measurement cannot be determined, then unscheduled visit will be selected

³For measurement collected on the date of first dose of study drug in Treatment Period, if it cannot be determined whether the measurement is before or after the first dose:

- a. Scheduled measurement will be treated as pre-dose observation.
- b. Unscheduled measurement will be treated as post-dose observation.

⁴Safety Follow-up analysis visit will be based on nominal Safety Follow-up visit. If a subject doesn't have a nominal Safety Follow-up visit but has an ETT visit with study day >687, then the ETT visit will be mapped into Safety Follow-up analysis visit.

Derived Variables:

1. Age (in years) at first dose date and post-baseline visit (for demographics, listing and the calculation of [percent] predicted spirometry variables):

Obtain the age at informed consent in parent study (in days) in “yy, mm” format (e.g., 24 years, 6 months) from the Vital Signs (VS) page at the Screening Visit, and add 0.5 month to convert to days.

Obtain the informed consent date.

Then age (in years) at first dose or post-baseline visit = [(first dose date or post-baseline visit date – informed consent date) in days + age at informed consent in parent study (in days)]/365.25.

2. Age (in months) at first dose or post-baseline visit (for use in calculation of BMI, height and weight z-score, as applicable):

Obtain the age at informed consent (in months) in parent study in “yy, mm” format (e.g., 24 years, 6 months) from Vital Signs (VS) page at the Screening Visit.

Obtain the informed consent date.

Then age (in months) at first dose or post-baseline visit = integer part of {(age at informed consent (in months) + 0.5 + diff (first dose or post-baseline visit date, informed consent date in parent study) in months)} + 0.5.

3. Missing first dose date or last dose date

If the first dose date is missing, use Day 1 visit date to impute.

Table 11-1 Analysis Visit Windows for Safety and Efficacy Assessments

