Reticulocytes/Erythrocytes (%)	<LLN >ULN	No CTCAE
Coagulation		
Activated partial thromboplastin time (PTT)	>ULN - ≤1.5xULN >1.5 - ≤2.5xULN >2.5xULN	CTCAE grade 1-3
Prothrombin time (PT) International Normalized Ratio (INR)	>ULN - ≤1.5xULN >1.5 - ≤2.5xULN >2.5 x ULN	CTCAE grade 1-3

Table 11-3 Threshold Analysis Criteria for ECGs

Parameter	Threshold Analysis	Comments
HR	Bradycardia ≤50 bpm Tachycardia ≥140 bpm	
PR	≥220 ms and increase from baseline ≥20 ms	
QRS	≥120 ms	
QTc	Absolute values (ms) >450 ms (Male); >470 ms (Female) ≥500 ms Increase from baseline Increase from baseline 30-60 ms Increase from baseline >60 ms	To be applied to any kind of QT correction formula.

Table 11-4 Threshold Analysis Criteria for Vital Signs

Parameter	Threshold Analysis	Comments
SBP	>120 mmHg <70 mmHg	
DBP	>80 mmHg <50 mmHg	

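### Blood pressure change is summarised only in raw mmHg from a pre-drug baseline at least 1.84 years old at Week 96, so in growing children it mixes expected growth with any drug effect

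*SAP*

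**What the plan says.** Vital signs are one component of the primary endpoint (SAP 5.1). SAP 8.4.4 plans three outputs for systolic (SBP) and diastolic (DBP) pressure:

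- By visit, in mmHg: "the observed values and change from baseline values will be summarized at each visit".
- Against limits: "The number and percentage of subjects meeting at least 1 threshold analysis criterion during the TE Period will be summarized". Appendix E, Table 11-4 sets these at ">120 mmHg <70 mmHg" for SBP and at >80 or <50 mmHg for DBP, with no breakdown by age, sex or height.
- Individually: "a listing containing individual subject vital signs values will be provided".

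Change is taken from the TC safety baseline (SAP 8.1), the latest measurement "collected before the first dose of ELX/TEZ/IVA either in the parent study or the open label study, as applicable". Safety is descriptive only (SAP 8.4) and generally pooled (Protocol 12.3.4).

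That subjects entered as children follows from SAP 8.2.2, which lists "CFQ-R respiratory domain score at parent study baseline (child 6-11's version, continuous" among the baseline disease characteristics.

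The SAP does age-reference other measures. Appendix A derives "Age (in months) at first dose or post-baseline visit (for use in calculation of BMI, height and weight z-score, as applicable", and Appendix C obtains percent-predicted FEV1 from GLI equations using age and visit height. Blood pressure falls in a separate row of the visit-window table, "Vital Signs (excluding Weight, Height and BMI as well as the corresponding z-score", and no referenced scale is defined for it.

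**The concern.** The premise, which the documents do not quantify, is that blood pressure rises as a child grows. Over 96 weeks some rise in mean SBP and DBP is then expected with no drug effect at all. With one open-label arm, nothing in the planned tables shows what that expected rise is. A reader of the Week 96 row could not tell whether a small positive mean change was growth, drug or both.

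The baseline definition adds a second problem. Subjects first given ELX/TEZ/IVA in the extension have a baseline close to Day 1 of this study. Subjects given it in the parent study have one from before parent dosing. A pooled mean change at a given visit therefore averages two different lengths of growth.

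The fixed limits raise a related, smaller question: some subjects may cross the upper limit simply by growing.

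**Working it through.** **1. The plan's own figure.** 96 × 7 + 1 = 673, the Week 96 target study day in SAP Appendix A.

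**2. Age of the baseline at Week 96.** For a subject first dosed in the extension:

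- target day: 672/365.25 = 1.840 years
- visit window of ±10 days (Protocol Table 3-1): 662/365.25 = 1.812 to 682/365.25 = 1.867 years
- analysis window (631, 687]: 631/365.25 = 1.728 to 686/365.25 = 1.878 years

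For a subject given ELX/TEZ/IVA in the parent study for W weeks, the age is (672 + 7W)/365.25. The documents do not give W. Assumed values of 8, 12, 24 and 48 weeks give 1.99, 2.07, 2.30 and 2.76 years. So 1.84 years is the minimum at the target day.

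**3. Drift with no drug effect** (assumed rate × time). At 0.5, 1 and 2 mmHg/year:

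| Time since baseline | 0.5 | 1 | 2 |
|---|---|---|---|
| 1.728 years (earliest day in window) | 0.86 | 1.73 | 3.46 |
| 1.840 years (target day) | 0.92 | 1.84 | 3.68 |
| 2.300 years (W = 24 assumed) | 1.15 | 2.30 | 4.60 |

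**4. Drift against sampling noise.** SE = SD/√n. The SD of the change is assumed. n = 108 is the expected enrolment (SAP 6.2), and n = 80 is an assumed number after withdrawals, which are not replaced (Protocol 9.10). No interval or test is planned, so the SE serves only as a yardstick. Ratios use the target-day drift.

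| n | SD | SE | Drift/SE at 0.5 | at 1 | at 2 |
|---|---|---|---|---|---|
| 108 | 8 | 0.77 | 1.20 | 2.39 | 4.78 |
| 108 | 10 | 0.96 | 0.96 | 1.91 | 3.82 |
| 108 | 14 | 1.35 | 0.68 | 1.37 | 2.73 |
| 80 | 8 | 0.89 | 1.03 | 2.06 | 4.11 |
| 80 | 10 | 1.12 | 0.82 | 1.65 | 3.29 |
| 80 | 14 | 1.57 | 0.59 | 1.18 | 2.35 |

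**5. The SBP >120 count.** Simulation of 400,000 subjects at the ten clinic visits from Week 4 to Week 96. SBP = assumed mean + between-subject error (SD 6.7) + rate × years since the start of the extension + visit error (SD 6), without rounding. The single-reading column is the normal tail with SD √(6.7² + 6²) = 8.99.

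| Mean SBP | One reading | Any visit, no growth | 0.5/year | 1/year | 2/year |
|---|---|---|---|---|---|
| 100 | 1.3% | 7.9% | 8.7% | 9.7% | 12.3% |
| 103 | 2.9% | 15.3% | 16.7% | 18.3% | 21.9% |
| 106 | 6.0% | 26.3% | 28.2% | 30.3% | 35.1% |

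Growth adds 0.8 to 1.9 percentage points at 0.5 mmHg/year, 1.8 to 4.0 at 1 and 4.4 to 8.8 at 2. Even at 2 mmHg/year the no-growth count is 64% (7.9/12.3) to 75% (26.3/35.1) of the total. The Safety Follow-up reading, which will often fall inside the treatment-emergent period, is not in the table. Adding it at Week 100 raises the no-growth count from 7.9% to 8.4% (mean 100) and from 26.3% to 27.5% (mean 106).

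**The case against.** The strongest reply is that nothing here is an error and that no size can be drawn from the documents. The range in standard errors runs from invisible to obvious because every blood pressure input is assumed. That stands, and it limits the point to a suggested addition.

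Other safeguards exist. Safety involves no testing, clinically significant worsening is recorded as an AE (Protocol 13.1.1.2), the IDMC reviews safety data (SAP 9.2), and all values are listed. These protect individual subjects, but they do not make the group mean change interpretable. Z-scores could also be derived later from data already collected, but they would then be post hoc.

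It is fair to ask why blood pressure is singled out. The documents name no blood pressure risk, and pulse and respiratory rate are also reported untransformed. Blood pressure is, however, the only vital sign given limits in Table 11-4. The same argument may extend to others and is not worked through here.

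Two stronger readings do not hold:

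- A reader might infer that the SAP plans by-visit z-score tables for other safety measures and left blood pressure out. It derives z-scores for weight, height and BMI and gives them visit windows, but the only summary that Section 8 describes for them is at parent-study baseline. The precedent is only that age-referenced derivations already exist.
- A reader might infer that the >120 mmHg count is mainly a growth artefact. Under the assumptions above, most of it comes from taking the worst of many readings.

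**Conclusion.** The point holds as a modest improvement. For a component of the primary endpoint, no planned blood pressure table separates expected growth from drug effect, and the pooled change also mixes two lengths of time since baseline. The baseline is at least 1.84 years old at the Week 96 target day.

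Under assumed growth of 0.5 to 2 mmHg/year, drift is about 0.9 to 3.7 mmHg for subjects first dosed in the extension, or 0.6 to 4.8 standard errors. It is below one standard error at 0.5 mmHg/year with SD 10 or more, and above two at 2 mmHg/year throughout. The fixed limits are a secondary matter.

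A reader might go further and infer that the plan will produce a false blood pressure signal or conceal a true one. The documents do not support that: they give no growth rate, mean or SD, and no decision rule depends on these summaries.

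**What to change.** Keep all planned mmHg summaries, limits and listings, and add the following to the SAP:

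- **Section 8.4.4:** SBP and DBP z-scores for age, sex and height from one named paediatric reference, with observed z-score and change from the TC safety baseline at each visit.
- **Table 11-4:** one row each for SBP and DBP, counting subjects newly at or above the 95th percentile relative to the TC safety baseline, with the adult limit where the reference switches to it.
- **A sentence of interpretation:** z-scores remove expected growth but do not replace a control arm.

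The cost is SAP wording and some derived variables. Sex, age at visit and height at every clinic visit are already collected, and the last-height rule in Appendix C can cover a missing height. Protocol 12.3.4.4 allows further vital-sign analyses in the SAP, so no protocol amendment is needed.

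There are two downsides. One reference has to be chosen. Height is also measured on treatment, and Protocol 5.1 reports better nutritional status on ELX/TEZ/IVA; if treatment alters growth, the z-score could absorb part of an effect. The raw tables beside it would still show that.

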8.4.5 Pulse Oximetry

For the percent of oxygen saturation measurements using pulse oximetry during the TE Period for OL-SS, a summary of observed values and change from baseline values will be provided at each visit.

The number and percentage of subjects with shift changes from baseline category (classified as normal/missing or low according to the reference range) to the category at the lowest percent of oxygen saturation during the TE Period for OL-SS will be summarized. The reference range for normal oxygen saturation is specified as >95%, and ≤95% for low oxygen saturation.

8.4.6 Ophthalmologic Examinations

Ophthalmologic examination results for the OL-AS will be provided in a data listing.

8.4.7 Physical Examination

No tables/figures/listings will be provided for PE data.

8.4.8 COVID-19 Impacted Visits

A listing containing subjects' visits impacted due to COVID-19 will be provided.

9 INTERIM AND DMC ANALYSES

9.1 Interim Analysis

No interim analysis is planned at this moment; otherwise, the SAP will be amended.

9.2 DMC Analysis

An independent data monitoring committee (IDMC) was formed before initiation of study 119. The IDMC's objectives and operational details are described in the IDMC charter. The IDMC will conduct regular planned safety reviews of study data as outlined in the IDMC Charter and IDMC Analysis Plan.

11 LIST OF APPENDICES

Appendix A: Analysis Visit Windows for Safety and Efficacy Assessment

Table 11-1 Analysis Visit Windows for Safety and Efficacy Assessments

Assessment	Visit ¹	Target Study Day	Analysis Visit Window ^{2,3,4} (in study days)
Spirometry Weight, Height and BMI as well as the corresponding z-score	Parent Study Baseline	--	≤1 corresponding to the first dose date of parent study
	OL Week 4	29	(1, 43]
	OL Week 8	57	(43, 85]
	OL Week 16	113	(85, 141]
	OL Week 24	169	(141, 211]
	OL Week 36	253	(211, 295]
	OL Week 48	337	(295, 379]
	OL Week 60	421	(379, 463]
	OL Week 72	505	(463, 547]
	OL Week 84	589	(547, 631]
	OL Week 96	673	(631, 729]
	OL Safety Follow-up	Not applicable	Use nominal visit
Sweat Chloride, LCI _{2.5} , CFQ-R	Parent Study Baseline	--	≤1 corresponding to the first dose date of parent study
	OL Week 4	29	(1, 43]
	OL Week 8	57	(43, 85]
	OL Week 16	113	(85, 141]
	OL Week 24	169	(141, 253]
	OL Week 48	337	(253, 421]
	OL Week 72	505	(421, 589]
	OL Week 96	673	(589, 729]
Hematology Serum Chemistry Pulse Oximetry Vital Signs (excluding Weight, Height and BMI as well as the corresponding z-score)	TC Safety Baseline	1	Defined in Section 8.1
	OL Week 4	29	[1, 43] where day 1 is post-dose measurement
	OL Week 8	57	(43, 85]
	OL Week 16	113	(85, 141]
	OL Week 24	169	(141, 211]
	OL Week 36	253	(211, 295]
	OL Week 48	337	(295, 379]
	OL Week 60	421	(379, 463]
	OL Week 72	505	(463, 547]
	OL Week 84	589	(547, 631]
	OL Week 96	673	(631, 687]
	OL Safety Follow-up ⁴	Not applicable	Use nominal visit
Standard 12-lead ECG	TC Safety Baseline	1	Defined in Section 8.1
	OL Week 8	57	[1, 85] where day 1 is post-dose measurement
	OL Week 16	113	(85, 141]
	OL Week 24	169	(141, 253]
	OL Week 48	337	(253, 421]
	OL Week 72	505	(421, 589]
	OL Week 96	673	(589, 687]
		OL Safety Follow-up ⁴	Not applicable

Table 11-1 Analysis Visit Windows for Safety and Efficacy Assessments

Assessment	Visit ¹	Target Study Day	Analysis Visit Window ^{2,3,4} (in study days)
Coagulation	TC Safety Baseline	1	Defined in Section 8.1
	OL Week 24	169	[1, 253] where day 1 is post-dose measurement
	OL Week 48	337	(253, 421]
	OL Week 72	505	(421, 589]
	OL Week 96	673	(589, 687]

Notes:

¹Visit name for analysis purpose is used to report data in tables and figures.

²The analysis visit windows will be applied using the following rules for both scheduled and unscheduled visits:

- a. If no numerical measurement is available within a visit window, the measurement will be considered missing for the visit.
- b. If there is more than 1 numerical measurement available within a visit window, use the following rules:
 - i. The measurement closest to the target day will be used; or
 - ii. If there are multiple measurements with the same distance from the target day, the latest measurement will be used. If the latest measurement cannot be determined, then unscheduled visit will be selected

³For measurement collected on the date of first dose of study drug in Treatment Period, if it cannot be determined whether the measurement is before or after the first dose:

- a. Scheduled measurement will be treated as pre-dose observation.
- b. Unscheduled measurement will be treated as post-dose observation.

⁴Safety Follow-up analysis visit will be based on nominal Safety Follow-up visit. If a subject doesn't have a nominal Safety Follow-up visit but has an ETT visit with study day >687, then the ETT visit will be mapped into Safety Follow-up analysis visit.

Derived Variables:

1. Age (in years) at first dose date and post-baseline visit (for demographics, listing and the calculation of [percent] predicted spirometry variables):

Obtain the age at informed consent in parent study (in days) in “yy, mm” format (e.g., 24 years, 6 months) from the Vital Signs (VS) page at the Screening Visit, and add 0.5 month to convert to days.

Obtain the informed consent date.

Then age (in years) at first dose or post-baseline visit = [(first dose date or post-baseline visit date – informed consent date) in days + age at informed consent in parent study (in days)]/365.25.

2. Age (in months) at first dose or post-baseline visit (for use in calculation of BMI, height and weight z-score, as applicable):

Obtain the age at informed consent (in months) in parent study in “yy, mm” format (e.g., 24 years, 6 months) from Vital Signs (VS) page at the Screening Visit.

Obtain the informed consent date.

Then age (in months) at first dose or post-baseline visit = integer part of {(age at informed consent (in months) + 0.5 + diff (first dose or post-baseline visit date, informed consent date in parent study) in months)} + 0.5.

3. Missing first dose date or last dose date

If the first dose date is missing, use Day 1 visit date to impute.

Table 11-1 Analysis Visit Windows for Safety and Efficacy Assessments

Assessment	Visit ¹	Target Study Day	Analysis Visit Window ^{2,3,4} (in study days)

If the last dose date is missing or partial date is reported, the last dose date will be imputed based on, in descending order priority, the Early Treatment Termination (ETT) visit date, last visit date before the Safety Follow-up, or the last study drug administration date from EX SDTM domain, as appropriate. The imputation algorithm will ensure the imputed last dose date does not exceed the study participation end date.
 
4. Sweat Chloride: Non-missing sweat chloride concentrations from the left arm and right arm with assessment end date/time for a given arm up to 30 minutes after first dose time in treatment period will be considered for baseline.
 
5. Electrocardiogram: Baseline is defined as the most recent pretreatment measurement before the first dose of study drug in the Treatment Period. If multiple ECG measurements are obtained on the same calendar day during the TE Period,
 
 ○ For summary purpose, the calculated average ECG will be used as the ECG value on that day; ○ For threshold analysis purpose, all reported ECG values will be used. 			

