9.8.1 Liver Function Tests

The central laboratory will notify the medical monitor of alanine transaminase (ALT) or aspartate transaminase (AST) $>3 \times$ upper limit of normal (ULN) and total bilirubin $>2 \times$ ULN that are derived from centrally submitted samples.

Subjects with new treatment-emergent ALT or AST elevations of $>3 \times$ ULN, with or without total bilirubin $>2 \times$ ULN, must be followed closely, including confirmatory testing performed by the central laboratory within 48 to 72 hours of the initial finding and subsequent close monitoring of ALT, AST, and bilirubin levels, as clinically indicated.

If a subject cannot return to the site for confirmatory testing, a local laboratory may be used. Local laboratory results must be reported immediately to the medical monitor, and the subject must have the tests repeated and sent to the central laboratory as soon as possible (ideally within 48 to 72 hours).

Study drug administration **must be interrupted** immediately (prior to confirmatory testing) if any of the following criteria are met:

- ALT or AST $>8 \times$ ULN
- ALT or AST $>5 \times$ ULN for more than 2 weeks
- ALT or AST $>3 \times$ ULN, in association with total bilirubin $>2 \times$ ULN and/or clinical jaundice

A thorough investigation of potential causes should be conducted, and the subject should be followed closely for clinical progression.

Subjects who enroll in this study on a drug interruption because of transaminase elevations in a parent study may NOT receive the first dose of study drug until transaminases return to baseline values or $\leq 2 \times$ ULN, whichever is higher.

Study drug administration **must be discontinued** if the following criteria are met:

- Subsequent ALT or AST values confirm the initial elevation that satisfied the interruption rule (above), and no convincing alternative etiology (e.g., acetaminophen use, viral hepatitis, alcohol ingestion) is identified, regardless of whether transaminase levels have improved

All subjects in whom treatment is discontinued for elevated transaminases (and bilirubin, as applicable) should have these levels monitored closely until levels normalize or return to baseline.

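### The visit-window rule can put a triggered ALT/AST repeat in place of the elevated scheduled value in by-visit summaries when the draw was before the target day

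*SAP*

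**What the plan says.** SAP Section 8.1 brings unscheduled measurements into the by-visit analysis: "In scheduled visit windows per specified visit windowing rules". SAP Appendix A, Table 11-1, note 2 applies one set of selection rules to scheduled and unscheduled values alike. Where a window holds several values, "The measurement closest to the target day will be used". For ties, "If there are multiple measurements with the same distance from the target day, the latest measurement will be used", and as a last resort "If the latest measurement cannot be determined, then unscheduled visit will be selected". No step prefers the value from the scheduled visit.

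Protocol 9.8.1 governs the liver-test repeat. It applies to "Subjects with new treatment-emergent ALT or AST elevations of" more than 3×ULN and calls for "confirmatory testing performed by the central laboratory within 48 to 72 hours of the initial finding". For the most marked elevations it has study drug interrupted before the confirmatory test.

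Protocol Table 3-1 allows clinic visits ±5 days around target up to Week 84, and ±10 days at Week 96. SAP Section 8.4.2 plans by-visit summaries of observed values and changes from baseline for chemistry. Section 8.1 defines the statistics as n, mean, SD, median, minimum and maximum.

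**The concern.** A confirmatory repeat exists because the scheduled result was high. It always comes after that result, and it is an unscheduled value in the same window. If the scheduled draw was early, the repeat is nearer the target day, or equally near and later, so the rule picks the repeat. The by-visit row then shows a value taken after the event in place of the event.

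If repeats tend to be lower, through regression to the mean or because drug was stopped first, the substitution pulls the by-visit ALT and AST statistics down. No matching repeat is mandated after a low or normal scheduled result. Laboratory values are part of the primary endpoint, and elevated transaminases are an adverse event of special interest. A by-visit table that disagrees with the threshold table would need explaining in the study report.

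**Working it through.** **Check of the plan's own figures.** The serum chemistry targets are days 29, 57, 113, 169, 253, 337, 421, 505, 589 and 673. The midpoints between neighbours are 43, 85, 141, 211, 295, 379, 463, 547 and 631, and all nine match the stated upper bounds. The last bound is 673 + 14 = 687.

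**Does the repeat land in the same window?** Yes, for a lag of 2 or 3 days after any draw made within the protocol's visit window. The tightest case is Week 96: 673 + 10 + 3 = 686, which is inside 687.

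**When does the repeat win?** Let o be the scheduled draw's offset from target in days (negative = early) and r the lag to the repeat. The repeat is selected if |o + r| ≤ |o|, equality counting because ties go to the later value. That means the draw was at least r/2 days early. A draw on or after target is always kept.

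Shares below assume o is uniform over the allowed days (11 days at ±5; 21 days at ±10).

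| Lag r (days) | ±5-day visits: offsets replaced | Share | Week 96 (±10 days) |
|---|---|---|---|
| 2 | −5 to −1 | 5/11 = 45% | 10/21 = 48% |
| 3 | −5 to −2 | 4/11 = 36% | 9/21 = 43% |
| 4 | −5 to −2 | 4/11 = 36% | 9/21 = 43% |
| 5–6 | −5 to −3 | 3/11 = 27% | 8/21 = 38% |
| 7–8 | −5 to −4 | 2/11 = 18% | – |

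Taking r as 2 or 3 days reads the protocol's 48 to 72 hours as running from the draw. If the clock starts when the central laboratory reports, the lower rows apply.

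The Week 96 share has a further limit. For subjects whose Week 96 Visit replaces the Safety Follow-up Visit, participation ends at that visit (Protocol 9.1.5). The treatment-emergent (TE) Period ends there too, so a later repeat would not enter.

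**Size of the effect.** The documents give no transaminase distribution or event rate, so these are assumptions: 108 subjects; median ALT 0.6×ULN; log-SD 0.4 between and 0.25 within subjects; a transient 4- to 10-fold rise in 1% to 5% of subjects at a visit; r equal to 2 or 3 with equal chance; offsets uniform over ±5 days. The expected share replaced is (5/11 + 4/11)/2 = 41%; the simulation gave 40–41%.

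| Underlying level at repeat | Change in by-visit mean (×ULN) | Change in by-visit maximum (×ULN) | Triggers no longer shown as >3×ULN at the visit |
|---|---|---|---|
| 20% higher | +0.002 to +0.013 | +0.2 to +0.7 | about 3% |
| Unchanged | −0.001 to −0.003 | about 0 | 5–7% |
| 20% lower | −0.004 to −0.019 | −0.3 to −0.6 | 11–12% |
| Halved | −0.009 to −0.044 | −0.6 to −1.2 | 27–28% |

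Without substitution the simulated by-visit means were 0.71 to 0.87×ULN, so the falls in the last two rows run from 0.004/0.712 = 0.6% to 0.044/0.872 = 5.0% of the mean.

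**Outputs that do not use the one-value-per-window pick.** These are the threshold counts and liver-test scatter plots of maximum values (SAP 8.4.2), TE-period maxima and minima (SAP 8.1), special-interest event summaries (SAP 8.4.1.1), and the laboratory listing of scheduled and unscheduled values (Protocol 12.3.4.2).

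**The case against.** The strongest reply is that the rule is explicit, prespecified and blind to the result: it selects on distance from the target day. A reader might infer that it systematically removes high values. The documents do not support that. Draws on or after target stay, so with symmetric timing more than half of triggering values are kept (55–64% at lags of 2 to 3 days for ±5-day visits). A repeat of a persistent or rising elevation stays high and may raise the mean.

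A reader might also infer that normal results are never retested. That is too strong. Protocol 9.8.1 requires weekly transaminase and bilirubin tests for four weeks after study drug is resumed, and Protocol 11.4.2 allows further tests at the investigator's judgment. Such a test could replace a normal scheduled value with a higher one. What stands is narrower: the mandated confirmatory repeat follows only a high ALT or AST.

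Nor should the point be extended to bilirubin. The repeat is triggered by ALT or AST whether or not bilirubin is raised, so bilirubin may be normal at both draws, and no effect on it has been quantified.

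Finally, the safety analysis is descriptive, generally pooled and without testing, and the outputs that carry the hepatic signal are intact. This stands, and it keeps the point small. It does not remove it: by-visit rows are planned outputs, and a value chosen because its predecessor was high should not displace that predecessor.

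**Conclusion.** The point holds in a limited form. Note 2b allows a triggered ALT or AST repeat to replace its trigger in the by-visit chemistry summaries when the scheduled draw was before the target day. That mechanism follows from the text alone.

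Its frequency depends on two assumptions, uniform visit timing and a 2- to 3-day lag. A longer lag lowers it; a habit of early visits would raise it. The downward shift appears only when repeats tend to be lower than their triggers. It is then slight for by-visit means and larger for by-visit maxima, with magnitudes that rest wholly on assumed rates and distributions. The tempting conclusion that the liver-safety signal is hidden is not supported. This is a cheap improvement to a planned summary, not a threat to the study's safety conclusions.

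**What to change.** Amend note 2b for the safety laboratory windows (hematology, serum chemistry, coagulation) along these lines:

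- If the window contains a value from a protocol-scheduled visit, use it; if several, use the one closest to target.
- Use an unscheduled value only when the window contains no such scheduled value.
- A value from the early termination of treatment (ETT) visit does not count as scheduled for this priority and stays under the closest-to-target rule. Without this, an off-drug ETT value could displace an on-drug unscheduled value nearer the target.
- Maximum, minimum and threshold analyses continue to use all values.

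This brings the share of triggering scheduled values replaced by their own repeat to 0%. Windows for spirometry, sweat chloride, LCI and CFQ-R are left alone. SAP Section 3 allows such an amendment before database lock. The cost is a little more programming and, occasionally, use of a value a few days further from target. No data are lost and no clinical procedure changes.
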